- WP3, coordinated by “Mario Negri” Institute (Milan, Italy): Survey on secondhand smoke and electronic cigarettes in Europe;
- WP9, coordinated by ISPO (Florence, Italy): Attributable mortality and morbidity to secondhand smoke in Europe;
- WP10, coordinated by Universidad Politécnica de Cartagena (Cartagena, Spain): Economic impact of secondhand tobacco smoke on morbidity and mortality and Return on Investment of Intervention.

Objectives of this cross-sectional study are:

- to estimate prevalence of current smokers, electronic cigarette users (and, for Italy, heat-not-burn cigarette users), and exposure to SHS and passive exposure to emissions from electronic cigarettes in selected European countries (WP3);
- to investigate the determinants of SHS exposure in those countries (WP3);
- to analyze the attitudes and perceptions of the adult European population towards policies to control tobacco and to limit SHS exposure (WP3);
- to study knowledge and beliefs of current smokers and the general adult population on the harmful effects of SHS (WP3);
- to compare smoking patterns, electronic cigarette use, and, particularly, SHS exposure between selected middle- and high-income countries in Europe (WP3);
- to compare smoking patterns, voluntary home smoking ban, and perception on the efficacy of smoking ban as a tobacco control policy between the new data in the selected European countries, and data from a companion pan-European survey conducted in 2010 (WP3);
- to assess: i) mortality attributable to SHS for lung cancer and ischaemic heart diseases among non-smoking adults; ii) morbidity (e.g., induction of asthma) attributable to SHS in non-smoking adults; iii) mortality attributable to SHS in children (e.g., Sudden Infant Death Syndrome [SIDS]); iv) morbidity (e.g., lower respiratory infections; asthma onset; acute otitis media) attributable to SHS in children (WP9);
- to quantify the economic burden associated to the exposure to SHS and e-cigarette aerosol in Europe (WP10).

METHODS

Study design

To achieve the aims of this study, we will conduct a face-to-face population-based cross-sectional survey in 12 strategically selected European countries (Bulgaria, England, France, Germany, Greece, Ireland, Italy, Latvia, Poland, Portugal, Romania, and Spain).

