The statistical analyses needed to achieve objectives related to WP9 will be conducted at ISPO. To achieve WP9 aims, researchers at ISPO will conduct a review of the scientific literature on the methods to estimate attributable mortality and morbidity (AMM) to SHS, using various research engines, including PubMed. Moreover, they will update the list of health effects and their corresponding relative risks (RR) in terms of mortality and morbidity causally linked to SHS included in the IARC Monograph on involuntary smoking [1]. Within WP9 we will assess mortality attributable to SHS for lung cancer, ischaemic heart diseases, and morbidity attributable to SHS (e.g., induction of asthma) in non-smoking adults. Moreover, among children we will assess mortality attributable to SHS (e.g., Sudden Infant Death Syndrome, SIDS, in children aged <1 year) and morbidity attributable to SHS (lower respiratory infections in children aged <3 years; asthma onset in children aged <14 years; acute otitis media in children aged <14 years). In order to estimate AMM to SHS, ISPO researchers will use: i) mortality and morbidity figures of SHS-related diseases in Europe, and ii) prevalence of exposure to SHS of the European population. Mortality and morbidity figures of SHS-related diseases in EU-28 will be obtained through the collaboration with the World Health Organization-Global Burden of Disease (WHO-GBD) algorithm. Prevalence of SHS exposure will be derived from data collected within the TackSHS survey in the 12 European countries considered. Eurobarometer surveys will be used to obtain prevalence of SHS exposure in the remaining EU-28 countries and to validate estimates from the TackSHS survey. Moreover, sensitivity analyses of AMM to SHS will be conducted varying different assumptions (e.g., using upper and lower 95% confidence limit of RRs or ORs from meta-analyses, using different hypotheses of susceptibility of current and ex-smokers to SHS, changing other assumptions).

Statistical analyses for WP10

The statistical analyses needed to achieve objectives related to WP10 will be conducted at the University of Cartagena. To accomplish WP10 objectives, researchers will evaluate policies aimed at reducing exposure to SHS across European countries, through the development of a model (Return On Investment – ROI – model) able to assess the cost-effectiveness, budget impact and a wider set of social return on investment metrics of these policies.

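### Must the plan fix now which TackSHS measure stands for children's exposure to secondhand smoke in the WP9 burden estimates?

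*Combined protocol and SAP*

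**What the plan says.** The Objectives and the section Statistical analyses for WP9 commit the project to two kinds of burden. One is adult, for example "mortality attributable to SHS for lung cancer and ischaemic heart diseases among non-smoking adults". The other concerns children: sudden infant death under 1 year, and then "lower respiratory infections in children aged <3 years; asthma onset in children aged <14 years; acute otitis media in children aged <14 years".

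Both share one exposure input, described as "prevalence of exposure to SHS of the European population". Its source is stated next: "Prevalence of SHS exposure will be derived from data collected within the TackSHS survey in the 12 European countries considered". Eurobarometer supplies exposure "in the remaining EU-28 countries and to validate estimates from the TackSHS survey". The Inclusion criteria set the survey's lower age limit at 15, so no child in any of the WP9 age bands answers the questionnaire.

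Three other statements bear on the point:

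- WP9 begins with methods work: its researchers "will conduct a review of the scientific literature on the methods to estimate attributable mortality and morbidity (AMM) to SHS".
- Its sensitivity analyses include "using different hypotheses of susceptibility of current and ex-smokers to SHS, changing other assumptions".
- Under Data collection, section C of the questionnaire covers exposure by setting. Its examples include homes, and private places with a specific mention of minors being present, alongside workplaces and public places.

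**The concern.** Child exposure has to be a proxy, or come from another source, and WP9 does not say which. Two choices that the wording does not rule out would go wrong in different directions:

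- **Any-setting exposure of respondents.** This counts workplaces and public venues. It overstates child exposure if children are exposed mainly at home.
- **Home exposure reported by non-smoking respondents only.** This suits the adult outcomes, which are defined in non-smokers. For children it drops the homes in which the respondent smokes. It understates exposure if those homes are smoked in more often.

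The attributable fraction rises with prevalence, so a poor choice would carry into the child results. It would reach the WP10 economic model only if child outcomes are among the diseases chosen there.

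There is also a question of timing. Data collection describes the questionnaire as already developed, while the WP9 review lies in the future. Privacy observance procedures has identifiers deleted within 4 months of the end of data collection. An item found missing after fieldwork could not then be added.

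**Working it through.** **1. The plan's own precision figure.** Study population gives about 1000 respondents per country, and Sample size computation gives a maximum standard error below 1.6 points. Under simple random sampling, SE = 100 × √(0.5 × 0.5 / 1000) = 1.58 points. The figure reproduces. It is stated for prevalence in the full country sample; nothing is claimed for children.

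**2. Sensitivity of the child result to the exposure measure.** The documents give no formula, relative risk (RR) or child prevalence, so all three are assumed here. The formula is AF = p(RR − 1) / [1 + p(RR − 1)]. The 20% to 60% range for exposed non-smokers comes from Background and Rationale.

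Any-setting exposure, with true child exposure set at 20% and RR 1.5:

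| p | AF | ratio to p = 20% |
|---|---|---|
| 20% | 0.10/1.10 = 9.1% | 1.0 |
| 40% | 0.20/1.20 = 16.7% | 1.8 |
| 60% | 0.30/1.30 = 23.1% | 2.5 |

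For 60% against 20%, the ratio is 2.8 at RR 1.2 and 2.3 at RR 2.0. The result depends on where the true value is placed. If child exposure is 30% (AF 0.15/1.15 = 13.0%) and any-setting exposure is 40%, the ratio is 16.7/13.0 = 1.3. If both are 20% it is 1.

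Non-smoking respondents only, with 20% of their homes smoked in, 40% or 60% of smokers' homes smoked in, and 20% or 30% of respondents smoking, at RR 1.5:

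| share smoking | smokers' homes | all-respondent p | AF, all | shortfall of 9.1% |
|---|---|---|---|---|
| 20% | 40% | 0.2 × 0.4 + 0.8 × 0.2 = 24% | 10.7% | 15% |
| 20% | 60% | 0.2 × 0.6 + 0.8 × 0.2 = 28% | 12.3% | 26% |
| 30% | 40% | 0.3 × 0.4 + 0.7 × 0.2 = 26% | 11.5% | 21% |
| 30% | 60% | 0.3 × 0.6 + 0.7 × 0.2 = 32% | 13.8% | 34% |

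The shortfall is zero if the two kinds of home are alike.

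**3. Whether the plan calls for either choice.** It does not. The any-setting choice would pool workplaces with homes, although section C records settings separately. The non-smoker choice would take a restriction that WP9 attaches to adults and apply it to children, who are introduced in a separate sentence without it. The exposure input is described for the European population, not for non-smokers. A third choice fits the text at least as well: the home items, or those on exposure with minors present, from all respondents including smokers. That choice has neither error above. What remains is that the answer is reported by proxy, and that a share of respondents is not exactly a share of children.

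**4. Precision under different choices.** Taken from all respondents, a home measure keeps n near 1000 and the standard error at 1.58 points. Restricted to respondents living with a child under 14 (assumed 10% to 30%, so n = 100 to 300), the maximum is 5.0 to 2.9 points per country, or 1.44 to 0.83 pooled over 12 countries. For infants (assumed 1% to 3%, n = 10 to 30) it is 15.8 to 9.1 points per country and 4.6 to 2.6 pooled. Infant exposure alone is therefore not estimable by country with useful precision, and adding an infant age band to the questionnaire would not change that.

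**5. Whether the data will exist.** The questionnaire is Annex 4, which is not in the supplied text. The examples for the demographic section do not mention children in the household, but they are only examples, and section C does mention minors. WP9 is one of the three work packages served by the survey, consortium partners helped develop the questionnaire, and the child outcomes and age bands stand in the same protocol. Nothing in the documents shows that a needed item is absent.

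**The case for a change.** The strongest case for a change is that a methods review can choose among the items collected but cannot create one. No sentence places the review before fieldwork, and mentioning minors in general does not separate the under-1, under-3 and under-14 bands. The open-ended clause in the sensitivity analyses does not name child exposure, and the Eurobarometer check is not said to cover it. A line in WP9 naming the measure would cost little.

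Much of this is true as description: WP9 does leave the measure unstated, and the timing is as described. It does not amount to a fault in the plan. The argument about a missing item rests on an annex that cannot be examined here. Deletion of identifiers adds little, because Privacy observance procedures keeps names for quality assurance and withdrawal; re-contact to collect more data is not a stated use even before deletion. Relevance and Implications promises European and country-specific information without mentioning children, so it creates no separate commitment to child estimates by country. If child outcomes do enter WP10, that section already asks for confidence intervals on model parameters, with deterministic and probabilistic sensitivity analyses, so imprecision in the exposure input would be carried through.

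**Conclusion.** The observation is correct, but no change to the plan follows. WP9 does not say which item, setting or respondents supply child exposure. Under the assumptions shown, an unsuitable choice could inflate the child attributable fraction by a factor of 1 to 2.5 at RR 1.5, or lower it by 0% to 34%. These figures describe choices that the plan does not make, with inputs that it does not give; they do not measure an error in it.

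Wording that says only that exposure is derived from TackSHS data leaves room for a sound measure. Section C covers the relevant settings, the methods review comes first within WP9, and the sensitivity analyses are open to varying this assumption. An analyst estimating childhood burden would turn to exposure at home or with minors present, without restricting to non-smoking respondents, or would use an external child source, and would report the choice with its precision. Writing that down now would record what competent analysts would do anyway. This conclusion rests on section C being carried out as its examples indicate; a questionnaire lacking any home or minors item would change it, but nothing supplied suggests that.

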The study methodology will be similar to a previous companion pan-European survey, conducted in 18 European countries in 2010 within an EU Seventh Framework Programme (FP7) Project, entitled “Pricing Policies And Control of Tobacco in Europe” (PPACTE; Grant Agreement HEALTH-F2-2009-223323) [21]. Briefly, in each country, the study sample will be representative of the general population aged 15 years and over in terms of age, sex, geographic area, and socio-economic characteristics. The multi-stage methodology will be used as the preferred sampling methodology. In the first stage, the primary unit of selection will be geographic area or voting centre. In the second stage, households or municipalities will be selected. In the last stage,

respondents will be chosen randomly, in order to be representative of the population. In those countries where adult respondents will be selected from electoral rolls, the quota method will be used to select minors (i.e., aged 15 to 17). Other methods, including stratified or simple sampling or quota methods, will also be accepted wherever it is not possible to conduct a multistage random sampling.

Selection of countries

For the present study, an appropriate sample of 12 European countries – all EU Member States (MS) – representing geographical, legislative and cultural variations across the EU, has been selected.

The selected European countries are the following: Bulgaria (BG), England (UK), France (FR), Germany (DE), Greece (GR), Ireland (IE), Italy (IT), Latvia (LV), Poland (PL), Portugal (PT), Romania (RO), and Spain (ES).

These countries were selected after taking into account several aspects, including: i) different geographical distribution; ii) different level of per capita income; iii) different national smoking prevalence [21]; iv) different adoption of tobacco control strategies at a national level (i.e., Tobacco Control Scale, TCS) [22]; v) different tobacco ban legislations [22]; vi) high population size; vii) inclusion in a previous PPACTE survey [21].

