According to geographic area, we considered countries from northern (IE, UK), central/western (DE, FR), central/eastern (BG, LV, PL, RO), and southern Europe (ES, IT, GR, PT). Moreover, the selection includes the 7 most populated EU MS (DE, ES, FR, IT, UK, PL, RO), and, among less populated countries, we prioritized middle-income countries (BG, RO). Finally, besides Germany, all the other countries were included in the 2010 PPACTE survey. Overall, the 12 selected EU MS represent 78.8% of the EU28 overall population.

Study population

In each of the 12 selected European countries, approximately 1000 individuals, representative of the general population aged 15 years and over in terms of age, sex, geographic area, and socio-economic characteristics, will be enrolled in this cross-sectional study. The final sample will therefore include a total of approximately 12,000 subjects.

Inclusion criteria

- individuals aged 15 years and over;
- individuals resident of the 12 selected countries;
- individuals able to understand and answer the questions of the questionnaire of the study in the country-specific language;
- individuals who formally accept to participate in the study.

Exclusion criteria

No specific exclusion criteria are considered.

Sample size computation

The sample size in each specific country will allow us to obtain prevalence estimates with a maximum standard error (SE) lower than $\pm 1.6\%$. Therefore, with such a sample size we will be able to provide stable prevalence estimates (with a relatively small 95% confidence interval), overall but also in each specific country.

Data collection

In each country, individuals will be surveyed by trained interviewers through face-to-face interviews using a structured standardized questionnaire. Data collection will be coordinated by DOXA, a leading market research organization and Italian branch of the Worldwide Independent Network/Gallup International Association (WIN/GIA), and performed in collaboration with its

European partners (see “Selection of the subcontractor performing data collection” paragraph). Whenever possible, data will be collected within computer assisted personal interviews (CAPI). Alternatively, paper and pencil (P&P) interviews will be accepted. Data collection will start once obtained the approval from the Ethics Committee of the 12 European countries involved in the study. The fieldworks will last two to three months in each country.

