At recruitment, information on survey characteristics will be given to all participants by suitably qualified professionals, who will be able to provide answers to any possible questions and to eliminate any concern respondents may have. This information will be provided through the Information Sheet (Annex 5 for adults and Annex 5bis for minors), and will be translated in various languages and provided to survey participants in a clear, jargon free way, using fully understandable terms and language. This document includes:

- the purpose of the information to be collected, including aims, methods and implications of the research;
- the extent to which personal data is used and accessed by various partners;
- the participant right to withdraw from participation in the study.

Although in EU countries, according to their current legislation, written consent is not mandatory for this type of study, following the request of the EC all participants will be asked to sign the informed consent form for participation in the study. Written informed consent will thus be obtained from each adult participant, and, in case of minors, representing approximately 5% of the survey sample, from one of their parents or legal tutors. In countries collecting data with CAPI method

(using computer or tablet), participants will have the possibility to tick an electronic document in order to express their willingness to participate in the study. No written signature will therefore be required. In those countries using P&P interviews, participants will be asked to sign the Consent Form (Annex 6 for adults and Annex 6bis for minors), containing personal details of participants. Wherever obtained, the signed document will be sent to the “Mario Negri” Institute by those DOXA partners using P&P interviews, and will be stored in “Mario Negri” Institute in archives with the access allowed only to part of the staff involved in the survey.

Privacy observance procedures

Survey data will be in electronic format. Only a selected number of pre-designated members of the data collection team will have access to the laptops protected password. Once data collection is complete, all data will be uploaded into a single database and reliably and completely deleted from the laptops.

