“Mario Negri” Institute, a non-for-profit private institute, had no obligation at a national or EU level, to launch a call for tender to select the most suitable market research organization, since “Mario Negri” Institute is not a contracting authority/contracting entity. However, in respect of the current practice at EU level, “Mario Negri” Institute requested a series of quotations from selected research market institute before the project submission. The 6th of February 2015, formal quotes have been required by e-mail four leading research market institutes offering a network of representatives throughout Europe with trained surveyors (i.e., DOXA, GfK-Eurisko, IPSOS and TNS). For a scenario of a face-to-face survey with 1000 participants in each of 12 countries, 12-14 minutes of interview, DOXA quoted € 225,000 + VAT for completion of this work, GfK-Eurisko requested € 315,000 + VAT, IPSOS requested € 325,680 + VAT and TNS requested € 421,000 + VAT. Therefore, DOXA provided by far the lowest quotation. Moreover, “Mario Negri” Institute has been collaborating with DOXA for several years to carry out annual national surveys on smoking since 2001. Therefore, the collaboration has been established before the beginning of the project. More importantly, in 2010, within the PPACTE project, “Mario Negri” Institute, in collaboration with DOXA and its European partners, already conducted a face-to-face representative survey on economic aspects of smoking in 18 European countries, using the same sample size, sampling methodology, and population proposed for the present investigation. A specific objective of the TackSHS survey refers to the comparison between data provided by the new survey and PPACTE data. Having DOXA as a subcontractor assures the identical country-specific sampling methodology. This allows us to obtain a more accurate comparison of selected smoking characteristics.

On the basis of the quotes received, the “best value for money” principle, and the long lasting collaboration with the Department of Epidemiology of “Mario Negri” Institute, DOXA has been identified as the best provider for the service.

Secondary used database

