For comparison purposes, a previously collected personal dataset will be analysed. These data come from a companion pan-European face-to-face survey, conducted in 2010 within the PPACTE Project, financially supported by the EC FP7. That survey was conducted in 18 European countries (Albania, Austria, Bulgaria, Czech Republic, Croatia, England, Finland, France, Greece, Hungary, Ireland, Italy, Latvia, Poland, Portugal, Romania, Spain and Sweden), on a total of 18,056 participants, representative for each country of the population aged ≥ 15 years. The study protocol was approved by the Institutional Review Board of the “Mario Negri” Institute. The procedures for recruitment of subjects, informed consent, data collection, storage and protection (based on anonymous identification code) were in accordance with the country specific legislation. This was ratified and signed by DOXA (the market research organization in charge of data collection) and each of its European partners. “Mario Negri” Institute was the owner/manager of the dataset, and therefore permission to use those data is not required.

Ownership of the data

Individual-level anonymous data sent from DOXA and its European partners, and stored at the “Mario Negri” Institute, will be the property of the study coordinator. Selected data will be made available to other TackSHS partners in order to pursue the aims of other WPs.

RELEVANCE AND IMPLICATIONS

One of the expected outcomes of the TackSHS European survey is the characterization of exposure to SHS and to e-cigarette aerosol in populations with different socioeconomic level and from various European countries. These results will have important implications on multiple aspects of public health and prevention for the European population and, when appropriate, will be disseminated in order to guide the development or the improvement of current smoke-free laws to protect the health of non-smokers.

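### The comparison with 2010 rests on an assurance of identical sampling within each country that no operating rule secures and no planned analysis checks

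*Combined protocol and SAP*

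**What the plan says.** Under Objectives, the protocol lists a comparison of smoking patterns, voluntary home smoking bans and the perceived efficacy of bans with the 2010 PPACTE survey.

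The section on selecting the subcontractor uses this comparison to justify its choice: "Having DOXA as a subcontractor assures the identical country-specific sampling methodology". It adds that the 2010 survey had the same sample size, sampling methodology and population as now proposed.

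The operating sections are looser:

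- **Study design:** "The study methodology will be similar to a previous companion pan-European survey". Multistage sampling is preferred, with this fallback: "Other methods, including stratified or simple sampling or quota methods, will also be accepted wherever it is not possible to conduct a multistage random sampling".
- **Data collection:** computer-assisted personal interviews (CAPI) are used where feasible. "Alternatively, paper and pencil (P&P) interviews will be accepted". Sampling method and response rate are among the country-level items recorded for the new wave.
- **Statistical analyses for WP3:** one dataset of common variables is built for the 11 shared countries. Period differences are tested by chi-square test, t-test and regression.
- **Secondary used database:** the 2010 survey is described as face-to-face, with 18,056 participants in 18 countries. No sampling method or recording mode is given by country.

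**The concern.** A trend between two cross-sectional surveys is credible only if each country drew and interviewed its sample in the same way both times. The plan recognises this and relies on the subcontractor to deliver it. Yet the rules the fieldwork partners will follow turn on what is feasible now, not on 2010 practice. A country could change its sampling method or move between paper and CAPI and still comply with the protocol.

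Within such a country, method and period would be the same variable. Adjusting for age, sex or education does not remove a difference caused by who was reached or how answers were recorded. The resulting bias would be in the trend itself, so a larger sample would not cure it and would make a false finding more likely to reach significance. At stake is the reading of any reported change in smoking, home bans or attitudes since 2010.

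**Working it through.** **1. The plan's own precision figure.** Sample size computation gives a maximum standard error (SE) below 1.6 points per country. With p = 0.5 and n = 1000 under simple random sampling, SE = √(0.25/1000) = 1.58 points, so the figure reproduces. For 2010, 18,056/18 = 1003 per country, which agrees with the claim of equal sample size.

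**2. What fixes the method in each country.**

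| Feature | Statement about 2010 | Rule for the new wave | Tied to the country's 2010 practice? |
|---|---|---|---|
| Sampling | Same methodology, asserted in the subcontractor section; not listed by country | Multistage preferred, others accepted if it is not possible | No |
| Interview | Face-to-face; CAPI or paper not stated | Face-to-face; CAPI where feasible, otherwise paper | No |
| Check at analysis | – | None in the WP3 plan | – |

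**3. SE of a country's change.** The documents give no baseline, so p = 0.30 is assumed, with 1000 per wave and simple random sampling: SE = √(2 × 0.3 × 0.7/1000) = 2.05 points.

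**4. Chance of a significant result with no true change.** For an artefact of b points in one country, at the two-sided 5% level:

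P = 1 − Φ(1.96 − b/SE) + Φ(−1.96 − b/SE)

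| Assumed artefact b | b/SE | P |
|---|---|---|
| 1 point | 0.49 | about 8% |
| 2 points | 0.98 | about 16% |
| 4 points | 1.95 | about 50% |
| 5 points | 2.44 | about 68% |

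The baseline matters little. A two-proportion test with pooled variance under the null gives 8.1%, 17.5%, 52.2% and 70.7% at a baseline of 25%, and 7.3%, 14.5%, 43.3% and 61.0% at 50%.

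**5. If the 11 countries were pooled.** The plan does not say whether the test is pooled, by country or both, so this is one possible analysis. With about 11,000 per wave, SE = √(2 × 0.3 × 0.7/11,000) = 0.62 points. Suppose 4 of 11 countries shift in the same direction:

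- By 4 points each: 4 × 4/11 = 1.45 points, z = 1.45/0.62 ≈ 2.35.
- By 2 points each: 4 × 2/11 = 0.73 points, z ≈ 1.2, which is not significant.

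Shifts in opposite directions would partly cancel.

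**6. Whether regression could separate the two.** Within one country it cannot, because method and period coincide. Across countries, a term for changed method could be estimated only by assuming the same true change in countries with changed and unchanged methods. The plan includes no such term.

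**The case against.** The best defence is that the fallback rules describe differences between countries. The assurance is about country-specific methods. A plan that lets some countries use quota sampling is compatible with each country repeating its own 2010 method. The fallback is also conditional on multistage sampling not being possible, and the protocol says outright that 2010 used the same sampling methodology. No section reports or plans a switch. This stands: a reader might infer that methods will change, or that the plan flatly contradicts itself, and the documents support neither. What remains is that the assurance has no matching rule and no check.

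The assurance also covers sampling only, so the choice between CAPI and paper does not contradict it. Both surveys are face-to-face, and some questions are kept identical to 2010. This stands too. Recording mode matters as a feature to tabulate, not as a breach of the assurance.

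A reader might also infer that a consent signature is new since 2010 and could have altered participation. The documents do not support that. The 2010 procedures, consent included, "were in accordance with the country specific legislation", which does not say whether consent was written. In the new survey, CAPI respondents tick an electronic document and need no signature.

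Finally, the artefact sizes are assumptions. That is correct, and small artefacts do little in a single-country test.

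**Conclusion.** The concern holds in a limited form. The plan claims identical sampling within each country, but its operating sections neither require this nor tie CAPI or paper to the country's 2010 practice. The analysis plan has no comparability check. A within-country change is permitted but not shown to be planned. If one occurred, it could not be told apart from real change.

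The size is conditional. With zero true change, the risk of a false significant result in one country runs from about 8% for a 1-point artefact to about 68% for a 5-point artefact, against a nominal 5%. This rests on an assumed prevalence of 30%, 1000 respondents per wave and simple random sampling. The documents give no artefact size, so the figures show sensitivity and do not forecast bias.

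Only the change-since-2010 objective is affected. The correction is cheap and worth making before fieldwork.

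**What to change.** 1. **Study design:** state that each of the 11 repeat countries uses its 2010 sampling method, with any deviation logged before fieldwork. This only turns the plan's own assurance into a rule.
2. **Data collection and Statistical analyses for WP3:** add interview mode to the country-level data. Tabulate sampling method, mode and response rate by country and wave, using 2010 records where available and otherwise stating the limitation. Report the period comparison for all 11 countries and again for those with unchanged sampling method and mode.
3. **Selection of the subcontractor:** replace the assurance of identity with a statement of what is actually held constant.

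Separately, Informed consent should be reconciled with itself. It says that "following the request of the EC all participants will be asked to sign the informed consent form for participation in the study" and then exempts CAPI respondents from a written signature. This is a point of consistency and does not bear on the comparison with 2010.

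The cost is one clause, one extra country-level item, one table and one further analysis. The availability of 2010 method data by country is not confirmed in the documents. Some countries may drop out of the restricted comparison, which widens its intervals. If 7 of 11 remained, the pooled SE at p = 0.30 would rise from 0.62 to √(2 × 0.3 × 0.7/7000) = 0.77 points. A gap between the two results could also reflect real differences between countries, so both should be shown and neither treated as a correction of the other.
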